## **2.0 OBJECTIVES**

### **2.1 Primary Objective**

Evaluate delayed recall as assessed by the Hopkins Verbal Learning Test-Revised (HVLT-R) 3 months after whole-brain radiotherapy modified as outlined (WBRT-HA/SIB) for brain metastases.

### **2.2 Secondary Objectives**

- 2.2.1 Evaluate time to neurocognitive failure as measured by cognitive decline on a battery of tests: the HVLT-R for free recall, delayed recall, and delayed recognition; the Controlled Word Association Test (COWAT); the Trail Making Test Parts A and B (TMT); the Medical Outcomes Scale-Cognitive Functioning Subscale (MOS); and the Mini-Mental Status Examination (MMSE) after WBRT-HA/SIB for brain metastases
- 2.2.2 Evaluate fatigue, as assessed by the Multidimensional Fatigue Inventory (MFI-20) after WBRT-HA/SIB for brain metastases.
- 2.2.3 Evaluate local control within the brain
  - 2.2.3.1 Evaluate local control of brain metastases treated with integrated boost
  - 2.2.3.2 Evaluate local control within the region of brain within the CTV receiving 20 Gy.
  - 2.2.3.3 Evaluate local control within the hippocampal regions.
- 2.2.4 Evaluate time to radiographic progression after WBRT-HA/SIB for brain metastasis.
- 2.2.5 Evaluate overall survival after WBRT-HA/SIB for brain metastasis.
- 2.2.6 Evaluate adverse events according to CTCAE criteria.
- 2.2.7 Evaluate health-related quality of life [as assessed by the Functional Assessment of Cancer Therapy with Brain Subscale (FACT-BR) and the Euroqol EQ-5D before and after (WBRT-HA/SIB)]

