patients, 1133 brain metastases were identified. Thirty-two patients had at least one brain metastasis within 5 mm of the hippocampi at the time of presentation. This yielded an incidence of 8.6%, allowing for the tightening of the estimated upper 95% confidence limit to 11.5%. From this, it can be concluded that 91% of newly diagnosed patients will be eligible for the WBRT that avoids the hippocampus. Patients who present with perihippocampal or hippocampal brain metastases will not be eligible for this protocol.

Although response rates after WBRT without hippocampal avoidance vary, complete or partial responses have been documented in more than 60% of patients in randomized controlled studies conducted by the RTOG, with intracranial disease control observed in approximately 50% of patients at 6 months (Khuntia 2006). It is currently not possible to provide a direct estimate of the risk of developing a metastasis after hippocampal avoidance WBRT, since such a comprehensive data set does not exist. However, if we assume that the risk of developing subsequent brain metastasis in the hippocampal avoidance region scales in the same proportion as that at presentation, from our data on the distribution of brain metastases relative to the hippocampus at presentation, we can conclude that a patient treated with hippocampal WBRT will derive 91.4% of the relative benefit of WBRT in terms of radiographically evident intracranial lesions, with a lower 95% confidence limit of 88.5% (Gondi 2010b). As the overall aim is to improve the interval to NCF decline, we hypothesize that hippocampal avoidance WBRT will provide a net gain in this endpoint. Furthermore, the modest increase in risk of intracranial progression with hippocampal avoidance may be partially compensated by the possibility of salvage with radiosurgery. Should salvage SRS be indicated for a perihippocampal recurrence, we expect that, given the very steep radiation dose falloff with SRS, some but not all of the benefit of hippocampal avoidance will be lost.

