##### **4.1 Required Evaluations/Management**

- 4.1.1 Neurocognitive assessments within 2 weeks before starting modified whole-brain radiotherapy (WBRT-HA/SIB): HVLT-R, COWAT, TMT, MOS, MMSE.
- 4.1.2 Fatigue assessment within 2 weeks before starting WBRT-HA/SIB: the Multidimensional Fatigue Inventory (MFI-20).
- 4.1.3 Scans Prior to WBRT-HA/SIB: See Section 6.0 for details.
- 4.1.4 Subjects will be screened for renal impairment prior to administration of gadolinium-based contrast agents (GBCA) as it is routinely done in the Radiology Department at UT Southwestern. A creatinine determination 28 days prior to the research MRI examination must be available to calculate an eGFR. An eGFR calculation may be repeated closer to the MRI appointment if the patient's medical condition has changed. An eGFR  $\geq 45$  mL/min/1.73m^2 is considered acceptable for administration of a standard weight-based dose of GBCA for research purposes.

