## **12.0 DATA COLLECTION**

### Summary of Data Submission

Item	Due
Demographic Form	Within 2 weeks of registration
Initial Evaluation Form	
Mini-Mental Status Exam	
Neurocognitive Evaluation Summary Form (HVLTR, TMT, COWAT)	Before the first treatment
Fatigue Evaluation Summary, FACT-BR, EQ-5D	
Follow-up Forms	3, 6, 9, 12, and 24 months after radiotherapy is completed
Mini-Mental Status Exam	
Neurocognitive Evaluation Summary Form (HVLTR, TMT, COWAT)	
Fatigue Evaluation Summary	
Quality of life Assessments (FACT-BR, EQ-5D)	As above
Progression MRI Scan & Report	Within 1 week of scan date

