#### 13.1.2 Secondary Endpoint

- 13.1.2.1 Cognitive function includes the HVLTR for free recall, and delayed recognition; the Controlled Word Association Test (COWAT); the Trail Making Test Parts A and B (TMT); the Medical Outcomes Scale-Cognitive Functioning Subscale (MOS); the Mini-Mental Status Examination (MMSE) after WBRT-HA/SIB for brain metastasis
- 13.1.2.2 Fatigue as measured by the Multidimensional Fatigue Inventory (MFI-20)
- 13.1.2.3 Time to radiographic progression
- 13.1.2.3 Overall survival
- 13.1.2.5 Adverse events based on CTCAE criteria

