#### 13.3.2 Secondary Endpoints

##### 13.3.2.1 Cognitive Function and Fatigue

All the secondary cognitive and fatigue endpoints will be analyzed similar to the primary endpoint. Additionally, the relationship between the change from baseline through 12 months in cognitive and fatigue endpoints will be evaluated using Spearman correlation coefficients.

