## Appendix III:

### Neurocognitive Function Assessments Background Information and Test Instructions

There are three immediate recall responses, one delayed recall response, and one delayed recognition response in the HVLTR. The response is the number of words the patient can recall out of 12 words for recall responses and the difference of the listed words correctly and incorrectly recalled for recognition response. The response from Trail Making Test, parts A & B is the time takes to finish each test less than 3 and 5 minutes, respectively. There are three responses for the COWAT, and each response is the number of words starting with a provided letter of the alphabet that the patient can produce in one minute.

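### Objective 2.2.1 is time to neurocognitive failure, but the plan defines no failure event and no time-to-event analysis; Trail Making non-finishers have no score, slowing takes the wrong sign, and the MOS is listed inconsistently

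*Combined protocol and SAP*

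**What the plan says.** Section 2.2.1 asks the trial to "Evaluate time to neurocognitive failure as measured by cognitive decline on a battery of tests", and names HVLT-R free recall, delayed recall and delayed recognition, COWAT, Trail Making A and B, MOS and MMSE. Section 1.4 gives the same idea as rationale: "As the overall aim is to improve the interval to NCF decline".

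The statistics section changes the quantity. Section 13.1.2.1 lists cognitive function on these tests, with no time element. Section 13.3.2.1 says: "All the secondary cognitive and fatigue endpoints will be analyzed similar to the primary endpoint". By 13.2 and 13.3.1 that means a one-sided, one-sample t-test on relative change. Section 13.3.2.1 adds that relations between cognitive and fatigue changes through 12 months "will be evaluated using Spearman correlation coefficients". Kaplan-Meier and Cox methods appear only for radiographic progression and overall survival.

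For Trail Making Parts A and B, Appendix III says that the response "is the time takes to finish each test less than 3 and 5 minutes, respectively". A test stopped at the limit leaves the reason and the furthest correct item. A test stopped at the sample stage leaves the reason.

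The MOS is in the baseline list of 4.1.1 ("HVLT-R, COWAT, TMT, MOS, MMSE") and among the secondary endpoints of 13.1.2.1 ("the Medical Outcomes Scale-Cognitive Functioning Subscale (MOS); the Mini-Mental Status Examination (MMSE) after WBRT-HA/SIB for brain metastasis"). Section 12 lists "Neurocognitive Evaluation Summary Form (HVLTR, TMT, COWAT" and, separately, the MMSE, but no MOS.

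**The concern.** A time-to-failure objective needs a definition of failure, a rule for patients who die before failing, and a method that yields times or cumulative rates. The plan has none of these for cognition, although it writes time-to-event methods out for two other endpoints. If the choices are left until the data have been seen, the result will depend on them. Section 1.7 intends a comparison with historical data to inform a decision on a phase III trial, so post hoc choices would weaken that use.

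Two details affect the cognitive results even when analysed as mean change. Trail Making patients who decline most may have no response to analyse, and for that test the copied formula turns worsening into apparent gain. The MOS is promised as an endpoint, but the documents do not agree on whether it is collected.

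**Working it through.** **1. Objective against analysis.** Section 2.2.1 asks for a time to failure; 13.3.2.1 yields a mean relative change and correlations. Neither gives a time to failure. No section sets a threshold for any test, a rule for combining tests, or a treatment of death. The only numeric decline rule is a fall of more than 5 HVLT-R points in section 1.1. It belongs to a cited trial and is not adopted here. Appendix III scores delayed recall out of 12, so a patient with a baseline of 5 or less could never meet it.

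**2. The plan's own figures.** Section 13.2 gives no figure for this objective. Its primary sample size is 18 analyzable and 50 registered, with SD 0.51, difference 0.60 − 0.30 = 0.30, one-sided alpha 0.05 and 80% power. The normal approximation, ((z₀.₉₅ + z₀.₈₀) × 0.51/0.30)², gives 17.87, so 18. Exact noncentral t gives 20, with power 77.3% at 18. Allowing for 60% deaths and 10% inevaluable, 18/(0.40 × 0.90) = 50.

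**3. Why the rule for death must be fixed in advance.** Let k of the 18 assessed patients have failed at 3 months; k is assumed. Suppose that the 60% die before that test without an observed failure, and that inevaluable survivors fail at the same rate as those assessed. The 3-month rate is k/18 if deaths are censored, 0.40 × k/18 if death competes, and 0.60 + 0.40 × k/18 if death counts as failure.

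| k (assumed) | Deaths censored | Death competes | Death counts as failure |
|---|---|---|---|
| 4 | 22% | 9% | 69% |
| 5 | 28% | 11% | 71% |
| 9 | 50% | 20% | 80% |

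The same data give three very different answers. Precision is also low: for 5 of 18 the exact 95% interval is 10% to 54%.

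**4. Trail Making non-finishers.** Assume a Part B baseline of 120 s and finishers 20% slower, at 144 s. A non-finisher scored at 300 s has slowed by (300 − 120)/120 = 150%. With a fraction f not finishing, mean slowing is (1 − f) × 20% + f × 150%:

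- f = 10%: 18% + 15% = 33%
- f = 20%: 16% + 30% = 46%
- f = 30%: 14% + 45% = 59%

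An analysis of completion times alone gives 20% whatever f is.

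For Part A, assume that some of 18 patients go from 60 s to not finishing in 180 s, a worsening of at least (180 − 60)/60 = 200%, and that the rest are unchanged. The mean worsening scored at the limit is 1 × 200%/18 = 11% for one such patient and 4 × 200%/18 = 44% for four. Among finishers it is 0% by construction.

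**5. Sign.** The formula in 13.2 is baseline minus follow-up, divided by baseline. For the Part B finisher above it gives (120 − 144)/120 = −20%, a negative decline. On a scale where positive values mean loss, that reads as improvement.

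**6. MOS.** It is named in 2.2.1, 4.1.1 and 13.1.2.1. It is absent from the battery in 1.5 (used at baseline and follow-up), the test descriptions in 11.2, the forms in section 12 and Appendix III. Appendix I has one generic neurocognitive row, marked before treatment and at every follow-up.

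**The case against.** The strongest reply is one of scope. This is a secondary objective of a phase II study planned on 18 analyzable patients, the primary objective is untouched, and the sentence in 1.4 is background rather than a listed objective. That stands as a limit on importance. It does not supply the missing event or analysis for an objective that 2.2.1 does list.

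A reader might infer that the objective cannot be answered at all. The documents do not support that. HVLT-R, COWAT, Trail Making and MMSE are collected at baseline and at five follow-up visits; what is missing is the definition and the analysis.

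A reader might also infer that the MOS is collected only at baseline, so that no change can be computed. That too goes beyond the text. The Appendix I row read with 4.1.1 could include the MOS at follow-up. Section 12 has no MOS form even at baseline. Absence from the Appendix III test order proves little, because the MMSE is absent there too and is still collected. What remains is an inconsistency.

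On Trail Making, no section says that unfinished tests are excluded. Section 11.2.2.2 gives the stopping limits, so the minimum time is known for a test stopped at the limit. The gap is a missing scoring rule, and the understatement arises if completion times are analysed as Appendix III defines the response.

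Finally, the plan proposes no curve that censors deaths, and the illustrations rest on assumed failure counts, baselines and non-completion rates. They show direction and sensitivity; they do not estimate this trial's bias.

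**Conclusion.** The point holds as a mismatch between objective and plan. Followed exactly, sections 13.1.2.1 and 13.3.2.1 never produce a time to neurocognitive failure, and this conclusion needs no assumption. The plan can be repaired with data that it largely collects already.

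The Trail Making understatement depends on how many patients do not finish: nil if all do, and 13 to 39 percentage points in the assumed Part B example with 10% to 30% not finishing (33 − 20 and 59 − 20). The sign reversal follows directly from applying the 13.2 formula to a test on which longer times are worse. For the MOS, the documents support only the statement that the lists disagree and need reconciling.

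**What to change.** 1. In 13.1.2.1 and 13.3.2.1, define failure for each test score as the first post-baseline assessment past a pre-specified worsening threshold in that score's harmful direction, set for that score's range. Do not carry the 5-point rule over to delayed recall. State whether failure is reported per test or for the battery. Report cumulative incidence of failure, with death as a competing event, at the scheduled visits through 24 months, and note that times are known only to the visit interval.
2. In Appendix III, score a Trail Making part stopped at the limit or for inability to do the task as 180 s (A) or 300 s (B). Count it as failure only if the patient completed that part at baseline.
3. Reverse the sign of the relative-change formula for Trail Making, so that positive values mean worsening as they do for recall.
4. Reconcile the MOS: add it to 11.2, section 12 and the follow-up battery, or delete it from 2.2.1, 4.1.1 and 13.1.2.1.

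The cost is protocol and SAP wording, slightly more analysis work and, if the MOS is kept, one more scale at existing visits. Reasons for stopped Trail Making tests are already recorded, so patients already tested can be rescored. The downsides are event times known only to the visit interval and reported decline that may look less favourable.

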## 3.0 PATIENT SELECTION

### 3.1 Conditions for Patient Eligibility

- 3.1.1 Pathologically (histologically or cytologically) proven diagnosis of a non-hematopoietic malignancy other than small cell lung cancer and germ cell malignancy.. Direct biopsy of CNS lesions is not necessarily required although could constitute an allowed site of tissue confirmation as medically prudent. Patients who have been disease free for more than 5 years prior to the appearance of CNS metastases should undergo repeat biopsy of either a systemic metastasis or the CNS metastases to confirm the recurrent malignancy.
- 3.1.2 Patients with measurable brain metastasis outside a 5-mm margin around either hippocampus
- 3.1.3 Patients with measurable brain metastasis who have not been or will not be treated with SRS or surgical resection (Note: These treatment options are only permitted at relapse)
- 3.1.4 History/physical examination within 28 days prior to registration
- 3.1.5 Patients must fall into RTOG recursive partitioning analysis (RPA) class I or II
- 3.1.6 Patients must have a life expectancy of at least 3 months.
- 3.1.7 Age  $\geq$  18 years
- 3.1.8 Karnofsky performance status  $\geq$  70
- 3.1.9 Patients must provide study-specific informed consent prior to study entry
- 3.1.10 Women of childbearing potential and male participants must practice adequate contraception
- 3.1.11 Women of childbearing potential must have a negative, qualitative serum pregnancy test  $\leq$  2 weeks prior to study entry
- 3.1.12 Patients who had radiosurgery  $>$  3 months prior to registration are eligible

### 3.2 Conditions for Patient Ineligibility

- 3.2.1 Patients with greater than 9 discrete metastases on MRI.
- 3.2.2 Patients with leptomeningeal metastases
- 3.2.3 Patients with measurable brain metastasis not resulting from small cell lung cancer and germ cell malignancy
- 3.2.4 Plan for chemotherapy or targeted therapies during WBRT or over the subsequent 7 days
- 3.2.5 Contraindication to MR imaging such as implanted metal devices or foreign bodies, severe claustrophobia AND patients unable to receive gadolinium contrast agents
- 3.2.6 Serum creatinine  $>$  1.4 mg/dl  $\leq$  28 days prior to study entry
- 3.2.7 Prior radiation therapy to the brain
- 3.2.8 Patients planning to undergo radiosurgery to any CNS lesion OR patients planning to have surgical resection of ALL of their CNS lesions
- 3.2.9 Patients with more than 2 (i.e., 3 or greater) uncontrolled or untreated extracranial sites of gross disease
- 3.2.10 Evidence of an active pulmonary, gastrointestinal, genitourinary, or other serious infection at time of enrollment.

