## SCHEMA

### Patient Population: (See Section 3.0 for Eligibility)

1. Pathologically proven diagnosis of a non-hematopoietic malignancy other than small cell lung cancer and germ cell malignancy.
2. Patients with less than 9 discrete metastases on MRI.
3. Measurable brain metastasis outside a 5-mm margin around either hippocampus
4. Have not been treated with SRS or surgical resection.
5. Patients with progressive brain metastases beyond a brain lesion previously treated with radiosurgery are eligible so long as at least 3 months has transpired from the radiosurgery procedure prior to registration.
6. RTOG RPA class I or II
7. Life expectancy of at least 3 months
8. Age  $\geq$  18 years
9. Karnofsky performance status  $\geq$  70
10. Two or fewer sites of uncontrolled or untreated sites of extracranial metastases
11. No active pulmonary, gastrointestinal, genitourinary or other serious infection at time of enrollment

Required sample size: 102

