## ELIGIBILITY CHECKLIST

(page 1 of 2)

Patient Initials \_\_\_\_\_ Case # \_\_\_\_\_

- \_\_\_\_\_(Y) 1. Does the patient have a pathologically confirmed diagnosis of a non-hematopoietic malignancy other than small cell lung or germ cell cancer?
- \_\_\_\_\_(Y) 2. Does the patient have measurable brain metastases outside a 5-mm margin around either hippocampus?
- \_\_\_\_\_(N) 3. Has the patient been treated with SRS or surgical resection?
- \_\_\_\_\_(Y) 4. Has the patient had a history/physical examination within 28 prior to registration?
- \_\_\_\_\_(Y) 5. Does the patient fall into RTOG RPA class I or II?
- \_\_\_\_\_(Y) 6. Does the patient have a life expectancy of at least 3 months?
- \_\_\_\_\_(Y) 7. Is the patient 18 years or older?
- \_\_\_\_\_(Y) 8. Does the patient have a KPS of 70 or greater?
- \_\_\_\_\_(Y) 9. Did the patient provide study-specific informed consent prior to any protocol-specified procedure(s)?
- \_\_\_\_\_(Y/NA) 10. If female, was there a negative serum or urine pregnancy test performed prior to treatment for women of childbearing potential?
- \_\_\_\_\_(N) 12. Does the patient have more than 9 discrete metastases on the MRI?
- \_\_\_\_\_(N) 13. Does the patient have leptomeningeal metastases?
- \_\_\_\_\_(N) 14. Is there a plan for chemotherapy or targeted therapies during WBRT or over the subsequent 7 days?
- \_\_\_\_\_(N) 15. Does the patient have a contraindication to MRI such as implanted metal devices or foreign bodies, severe claustrophobia and unable to receive gadolinium contrast agents?
- \_\_\_\_\_(N) 16. Does the patient have serum creatinine  $> 1.4 \text{ mg/dl} \leq 28$  days prior to study entry?
- \_\_\_\_\_(N) 17. Is the patient planning to undergo radiosurgery to any CNS lesion or planning to have surgical resection of all of their CNS lesions?
- \_\_\_\_\_(Y) 18. Does the patient have 2 or fewer sites of uncontrolled or untreated extracranial gross disease?

\_\_\_\_\_ (N) 19. Does the patient have an active pulmonary, gastrointestinal, genitourinary or other serious infection at time of enrollment?

\_\_\_\_\_ (Y) 20. For patients with progressive brain metastases beyond a brain lesion previously treated with radiosurgery, has at least 3 months transpired from the radiosurgery procedure?

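### The eligibility rules both admit and bar patients with earlier radiosurgery, and nothing says which rule prevails

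*Combined protocol and SAP*

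**What the plan says.** Three places admit earlier radiosurgery.

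- Schema item 5: "Patients with progressive brain metastases beyond a brain lesion previously treated with radiosurgery are eligible so long as at least 3 months has transpired", counted to registration.
- Eligibility Checklist item 20, required answer Y: "Y) 20. For patients with progressive brain metastases beyond a brain lesion previously treated with radiosurgery, has at least 3 months transpired" since the procedure.
- Section 3.1.12 admits patients whose radiosurgery was more than "3 months prior to registration are eligible".

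Four places bar it.

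- Section 3.2.7 lists as an exclusion: "Prior radiation therapy to the brain".
- Checklist item 3, required answer N: "N) 3. Has the patient been treated with SRS or surgical resection".
- Schema item 4: "Have not been treated with SRS or surgical resection".
- Section 3.1.3: "Patients with measurable brain metastasis who have not been or will not be treated with SRS or surgical resection", with a note that these options are open only at relapse.

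Section 5.1.1 has the enrolling investigator sign the checklist to confirm that every criterion is met, and 5.1.4 has CRO personnel confirm eligibility. Neither section ranks the clauses, and no other text does.

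**The concern.** Radiosurgery is radiation to the brain, so 3.2.7 as worded excludes the same patients whom 3.1.12 declares eligible. Site staff have no written rule to apply. Enrolling such a patient breaches a stated exclusion and needs a disqualifying answer on the signed checklist. Refusing turns away a group that the protocol names as eligible. Two investigators could decide the same case differently, and each could cite the protocol. The trial's population is then not fully defined by its own text on a point that bears on earlier brain treatment, in a study whose primary endpoint is memory.

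**Working it through.** No arithmetic applies. The check is to set the clauses side by side and run test patients through them.

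| Clause | Effect on earlier radiosurgery | Interval | Framed around progression beyond the treated lesion? |
|---|---|---|---|
| Schema item 5 | admits | at least 3 months, to registration | yes |
| Checklist item 20 (Y) | admits | at least 3 months, end point not stated | yes, as a conditional question |
| 3.1.12 | admits | more than 3 months, to registration | no |
| 3.2.7 | bars | none | no |
| Checklist item 3 (N) | bars, at patient level | none | no |
| Schema item 4 | bars on its face | none | no |
| 3.1.3 | bars on its face; could be read lesion by lesion | none | no |

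**Patient A: radiosurgery 4 months before registration, now with new metastases.** This patient passes Schema item 5, checklist item 20 and 3.1.12. The same patient fails 3.2.7, and the truthful answer to checklist item 3 is Y where N is required. The 5.1.1 signature therefore cannot be given truthfully.

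**Patient B: as A, but at exactly 3 months.** Schema item 5 and checklist item 20 are satisfied. Section 3.1.12 is not, because it needs more than 3 months. Even among the admitting clauses there is no single answer.

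**Patient C: radiosurgery more than 3 months ago, no progression beyond the treated lesion.** Section 3.1.12 admits on its wording. Schema item 5 does not reach this patient, and checklist item 20 does not address the case.

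**Patient D: no earlier radiosurgery.** Checklist item 20 accepts only Y, so this patient has no proper answer. Item 10 shows that the form can offer Y/NA.

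There is also a gap in the checklist. Items 16 and 17 correspond to 3.2.6 and 3.2.8, and no item in the checklist as supplied asks about 3.2.7. The numbering runs from 10 to 12, but a missing item 11 may be only an artefact of the supplied text, so I place no weight on it.

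**The case against.** The strongest reply is that the intent can be recovered. Three clauses set a waiting period for earlier radiosurgery, which would be pointless if 3.2.7 covered radiosurgery. Schema item 5 directly follows item 4 and reads naturally as its exception. Section 3.2.7 may mean earlier whole-brain or other conventional radiotherapy, and 3.1.3 may concern only the lesions now to be treated. Since the checklist seems to pass over 3.2.7, the block at registration rests mainly on item 3.

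Most of this stands as a reading of intent, and I accept that admission is the likely aim. It does not remove the conflict. None of it is written. Checklist item 3 asks about the patient, although item 17 shows that the drafters could write about lesions when they meant to. The relapse note in 3.1.3 may refer to salvage after protocol treatment, and it appears in neither 3.2.7 nor item 3. Intent also cannot settle patient B. For patient C, 3.1.3 read lesion by lesion may already exclude someone whose only disease has had radiosurgery, but that again is inference.

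A reader might also infer that previously treated lesions will be re-irradiated without limit, because 6.4.3 gives every metastasis seen on MRI a target volume. That would need such a patient to be enrolled, the old lesion to be still visible, and the physician to class it as a current metastasis. The documents settle none of these. Whether an old lesion is boosted is a separate question for the investigators and forms no part of this point.

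**Conclusion.** The point holds: the eligibility text is wrong as written. Section 3.2.7 and checklist item 3 bar without exception a group that Schema item 5, checklist item 20 and 3.1.12 admit, and the admitting clauses disagree on the interval and on progression. This is a working enrolment rule that fails when it is followed literally, so it should be corrected, although the remedy is small.

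Its size cannot be put in numbers. A reader might infer that ineligible patients have already been enrolled, or that the primary result is biased or the sample size wrong. The documents do not support that. They do not say how many of the 32 pilot patients, or of those still to come, had earlier radiosurgery, and the calculation in 13.2 does not depend on it.

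The conclusion rests on two things: radiosurgery counts as radiation therapy to the brain in the ordinary sense, and no order of precedence is stated anywhere in the documents.

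**What to change.** 1. Add the same words, *except radiosurgery allowed under 3.1.12*, to 3.2.7, 3.1.3, Schema item 4 and checklist item 3. Leave the bar on earlier surgical resection as it is. Limiting these clauses to lesions treated on protocol would be a mistake: a resected lesion is no longer a target, so patients with earlier resection, whom no current clause admits, could enter.
2. Use one interval and one progression condition in 3.1.12, Schema item 5 and checklist item 20. For example: *metastases progressing other than at a site already given radiosurgery, with at least 3 months from that procedure to registration*.
3. Code checklist item 20 as Y/NA, and add a checklist item for 3.2.7 carrying the same exception.
4. Check the 32 patients already enrolled for earlier radiosurgery and list any found.

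The cost is a wording amendment to seven eligibility clauses, one new checklist item and a chart check of 32 patients. No extra patients are needed and the analysis does not change.
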